1.3. Study Drug (MLN8237, alisertib)

1.3.1. Aurora A Kinases and the Aurora A Kinase Inhibitor MLN8237

MLN8237 is a selective small molecule inhibitor of Aurora A kinase that is being developed for the treatment of advanced malignancies. Aurora A kinase belongs to a highly conserved family of serine/threonine protein kinases that also includes Aurora B and Aurora C. Aurora A and Aurora B are expressed in all actively dividing cells, while Aurora C expression is largely restricted to dividing germ cells (Nigg et al, *Nature Reviews Molecular Cell Biology* 2001). Aurora A localizes to centrosomes and the proximal mitotic spindle during mitosis where it functions in a diverse set of mitotic processes. Aurora A overexpression in human cancers has been correlated with increased aneuploidy and centrosome amplification (Sen et al, *Journal of National Cancer Institute* 2002). Forced overexpression of Aurora A kinase in experimental models results in the transformation of normal cells, suggesting that Aurora A overexpression may be oncogenic. In a number of different experimental systems, Aurora A inhibition leads to mitotic delays and severe chromosome alignment and segregation defects, followed by cell death (Hoar et al, *Molecular & Cell Biology* 2007). Overall, the essential role of Aurora A in mitotic progression and its dysregulation in certain cancers made it an attractive therapeutic target, and therefore has been initially developed for treatment of a wide variety of tumor types. MLN8237 has demonstrated activity against a variety of nonclinical solid tumor and hematological malignancy models grown in vitro and in vivo (Goldberg et al, *Blood* 2010), as described below. MLN8237 is also expected to be toxic to proliferating normal tissues, such as the bone marrow, gastrointestinal (GI) epithelium, and

hair follicles because any cell that is in mitosis, where Aurora A is expressed and active, should be susceptible to the effects of an Aurora A kinase inhibitor.

1.3.2. Preclinical Experience with MLN8237

1.3.2.1. In Vitro Studies. MLN8237 is an adenosine triphosphate (ATP)-competitive and reversible inhibitor of Aurora A kinase in vitro with an inhibition constant (K_i) of 0.43 nM. In cultured HCT-116 human colorectal tumor cells, MLN8237 produces 50% inhibition of Aurora A kinase activity at a concentration of 6.7 nM. It is approximately 200-fold more selective for Aurora A kinase than the structurally related family member, Aurora B kinase (half maximal inhibitory concentration [IC_{50}] = 1534 nM). Moreover, in enzyme assays, MLN8237 is selective for Aurora A kinase when compared to other kinases and receptors. MLN8237 has affinity for the gamma acid alpha 1 (GABA_A $\alpha 1$) receptor benzodiazepine (BZD) binding site (K_i = 290 nM). The consequences of GABA_A binding in rat and dog safety pharmacology studies are discussed below.

Consistent with the mechanism of action for an Aurora A kinase inhibitor, MLN8237 treatment results in formation of abnormal mitotic spindles, an accumulation of mitotic cells, and a decrease in the proliferation of a broad range of tumor cell lines grown in culture.

The in vitro antiproliferative effect of MLN8237 was quantified in tumor cell lines derived from a variety of malignancies, including colon (3 cell lines), breast (1 cell line), lung (1), ovary (1), prostate (1), pancreas (1), and lymphoid (1). MLN8237 inhibited proliferation with lethal concentrations for 50% cell-growth inhibitor concentrations (GI₅₀ values) ranging from 16 to 469 nM, demonstrating that MLN8237 is a potent inhibitor of proliferation in diverse human tumor cell lines.

1.3.2.2. In Vivo Studies

MLN8237 has demonstrated broad antitumor activity in a diverse array of experimental human tumor xenografts when dosed QD or BID. These include 2 colon models (HCT-116 and DLD-1), 2 lung models (H460 and Calu-6), 1 breast model (MDA-MB-231 FP4), 1 prostate model (CWR22 RV-1 Luc1.17) and 4 DLBCL models (Ly19, WSU, Ly7, PHTX-22-06). Statistically significant tumor growth inhibition (TGI) was observed with MLN8237 given at 30 mg/kg QD or less in all models but the Calu-6 model. At 20 mg/kg BID or less, statistically significant TGI was observed in all models tested, including Calu-6. Taken together, these results demonstrated that MLN8237 has broad antitumor activity in many experimental human tumor models.

To define the plasma concentration of MLN8237 that inhibits Aurora A, the relationship between pharmacokinetics (PK) and pharmacodynamics was assessed at the steady-state concentration (C_{ss}). Steady-state MLN8237 concentrations were achieved using osmotic mini-pumps implanted subcutaneously (SC) in mice bearing HCT-116 xenografts. The relationship between the C_{ss} of MLN8237 and the tumor mitotic index fit the sigmoid maximum effect (E_{max}) model with an estimated efficacious concentration producing 90% of the maximal possible response (EC₉₀) of approximately 1 μ M.

The HCT-116 tumor model was also used to determine the antitumor activity of MLN8237 given either QD or BID. MLN8237 demonstrated dose-dependent TGI whether administered QD or BID. TGI with BID administration of 3 mg/kg (TGI = 70%) and 10 mg/kg (TGI = 102%) was greater than with QD administration when measured on the last day of treatment (Day 21).

The relationship between efficacy and systemic exposure was investigated using osmotic mini-pumps implanted SC to deliver sustained release of MLN8237 over 12 days to HCT-116 xenografts. The relationship between the efficacy (TGI) on Day 12 and the average plasma concentration (C_{avg}) values on Days 1, 3, 6, 8 and 12 fit the sigmoid E_{max} model. At a C_{avg} of 1 μ M sustained exposure in the 10 mg/mL group the TGI was 88.3%, which was between that observed in the 10 mg/kg (TGI 82.1%) and 30 mg/kg (TGI 93.1%) orally dosed groups.

1.3.3. Safety Pharmacology, Toxicology, and Drug Metabolism

Safety pharmacology studies evaluating the central nervous system (CNS) and cardiovascular effects of MLN8237 did not reveal significant adverse effects at the exposures anticipated to be required for human efficacy. MLN8237 has a low potential to prolong the QT interval on the electrocardiogram (ECG), based on its low in vitro activity against the potassium ion channel encoded by human ether-à-go-go related gene (hERG) and its lack of an effect on the QTcV interval in dogs. MLN8237 had minimal activity (< 40% inhibition) against all receptor ligand interactions examined except GABA α 1 benzodiazepine. Although MLN8237 did elicit behavioral CNS effects attributed to its binding to the GABA α 1 benzodiazepine, these effects occurred at dose levels which exceeded the repeat-administration daily oral maximum tolerated dose (MTD) of MLN8237.

The predominant effects of MLN8237 in Sprague-Dawley rats included peripheral blood cytopenias secondary to myelosuppression and increased mitotic figures/single cell necrosis (apoptosis) in tissues with a high basal cellular replication rate, consistent with the known mechanism of action of MLN8237. These effects were also the effects that predominated in repeat-dose studies in beagle dogs. CNS effects, consistent with the activity of MLN8237 at the GABA α 1 benzodiazepine receptor, were observed only in beagle dogs following a single oral dose of 5 mg/kg, which exceeds the daily oral repeat-administration MTD in this species.

MLN8237 is metabolized by multiple phase I (cytochrome P450 [CYP]3A4, CYP2C9, CYP2C19, and CYP1A2) and phase II (uridine diphosphate glucuronosyltransferase [UGT] 1A1, 1A3, and 1A8) enzymes. Using human liver microsomes with the appropriate cofactors, the percent contribution of CYP and UGT was calculated to be 13.1% and 86.9%, respectively, showing that CYP isozymes play a minor role in the metabolism of MLN8237. MLN8237 is unlikely to inhibit the 5 major CYP enzymes, 1A2, 2C9, 2C19, 2D6, and 3A4/5 ($IC_{50} > 100 \mu M$) when administered at the projected human efficacious dose. MLN8237 is not a mechanism-based inhibitor of CYP3A4/5. MLN8237 inhibited the P-glycoprotein (Pgp)-mediated efflux of paclitaxel (Taxol[®]) in Caco 2 cells with an IC_{50} of 4.0 μM .

Detailed information regarding the nonclinical pharmacology and toxicology of MLN8237 may be found in the IB.

1.3.4. Clinical Experience

Clinical experience with MLN8237 (alisertib) includes phase 1 and 2 studies in both solid tumors and heme lymphatic malignancies, described below. A phase 3 study in Peripheral T-cell Lymphoma (PTCL) began in early 2012.

MLN8237 for clinical studies is being developed in 2 dosage formulations: enteric-coated-tablet (ECT), and oral solution (OS: for pediatric use). Initial studies employed a powder-in-capsule (PIC) formulation, and more recent studies using current formulations all have evaluated safety, PK, relative bioavailability (in reference to the PIC), and antitumor activity after administration of the ECT formulation.

Using the ECT formulation, the dose-escalation, phase 1 portion of an ongoing study, C14007, has evaluated multiple dose levels from 10 to 60 mg BID for 7 days in repeat, 21-day cycles and 50 mg BID has been determined to be the MTD.

In Study C14007, which includes a phase 1 dose escalation using the same ECT formulation employed in this study, multiple dose levels up to 840 mg total cycle dose (60 mg BID for 7 days) were evaluated. At the maximum administered dose of 60 mg BID for 7 days administered to patients with advanced solid tumors, 3 patients (out of 3 enrolled) developed myelosuppression during the treatment-free period which was considered intolerable and above the MTD of 50 mg BID. In summary, 700 mg total cycle dose (eg, 50 mg BID administered daily for 7 days) represents the ceiling for dose escalation in these combinations with MLN8237 planned for this current study.

The predominant toxicities reflect the mechanism of action in proliferating tissues (bone marrow, GI epithelium, and hair follicles). The suggested management of these toxicities is based on standard clinical paradigms for an anti-proliferative chemotherapeutic agent. Using a treatment-free period for recovery between each cycle of drug administration, the clinical experience from multiple phase 1 through 2 studies indicate that major toxicities can be managed to allow repeat treatment cycles over periods extending beyond 12 months.

MLN8237 is structurally related to the benzodiazepines (BZD) (eg, diazepam, lorazepam) and also has activity against the GABA α 1 BZD receptor. BZD-like effects (eg, somnolence, confusion, memory loss) have been observed to be associated with the onset of maximal plasma concentration (eg, T_{max} [time to maximum plasma concentration]). CNS effects associated with peak plasma levels have been generally managed by administration of divided doses (eg, BID administration), although dose reductions have sometimes been required. While CNS effects attributed to MLN8237 were also

generally reversible and manageable by dose delay or reduction, the causal relationship, and thus optimal approach to management, were sometimes confounded by diverse causes including, but not limited to, concomitant medications (eg, narcotic analgesics, antianxiety medications), comorbidities (eg, infection, anemia, electrolyte abnormalities), or progressive malignancy (eg, brain metastases).

The clinical experience with MLN8237 includes treatment with multiple doses and schedules as described in the IB.

1.3.5. Pharmacokinetics

Based on an integrated assessment of the currently available PK data from PIC formulation across two solid tumor studies C14001 and C14002, it can be concluded that MLN8237 absorption is fast, with overall median T_{max} of 2 hours postdose. Overall mean steady-state terminal half-life following multiple dose administration in patients with non-hematologic malignancies was 23 hours. The overall mean peak/trough ratios were 2.5 and 5.2 for BID and QD dosing, respectively. The overall mean accumulation ratios were 2.9 and 1.8 for BID and QD dosing, respectively. Pharmacokinetic steady-state conditions were approximately achieved by Day 7 following daily oral administration. The steady-state exposure of MLN8237 increases approximately in a dose proportional manner over the range from 5 to 200 mg daily dose. Pharmacokinetic variability was high following administration as PIC (%CV in steady-state dose-normalized AUC_{0-24hr} of 78%). At the recommended phase 2 dose of 50 mg BID, the mean steady-state average concentration ($C_{ss,avg}$) exceeded the preclinical projected efficacious plasma concentration associated with saturating levels of pharmacodynamic and antitumor activity in HCT-116 mouse xenograft studies (1 μ M). The pharmacokinetic properties of MLN8237 in Protocol C14003 in patients with hematologic malignancies are generally consistent with those observed in patients with non-hematologic malignancies.

Glucuronidation is expected to be a major route of MLN8237 clearance and in vitro metabolism studies indicate that UGT1A1 is a contributor to MLN8237 glucuronidation. Preliminary results of dose-normalized steady-state exposure of MLN8237 by UGT1A1 genotype are available in 67 patients in Protocols C14001 and C14002. The geometric mean of dose-normalized steady-state AUC_{0-24hr} in *28/*28 genotype group ($N = 9$) was approximately 40% higher than that observed in the wt/wt genotype group ($N = 36$).

The MLN8237 molecules exhibits pH-dependent solubility, and the variability in gastric pH likely represents an important source of variability in MLN8237 oral absorption following administration of an immediate release formulation like the PIC. Emerging clinical data from enteric-coated tablet (ECT) formulation indicated that the steady-state systemic exposures of MLN8237 administered as the ECT

formulation are generally comparable to those observed with the PIC formulation. Based on preliminary results from 14 patients who received either ECT or PIC in a crossover design, the relative bioavailability of the ECT formulation in reference to the PIC formulation is estimated to be approximately 90%. Therefore the MTD of 50 mg BID determined for the ECT formulation in protocol C14007 is consistent with the estimated relative bioavailability of ECT versus PIC and the PIC MTD of 50 mg BID. These findings support continued use of the ECT formulation in the ongoing and future clinical development of MLN8237.

Further details regarding the clinical PK of MLN8237 are provided in the MLN8237 Investigator Brochure.

1.3.6. Potential Risks and Benefits

The safety risks of MLN8237 (alisertib) treatment are: (1) leukopenia, neutropenia, febrile neutropenia, and lymphopenia with a potential increased susceptibility to infection, (2) thrombocytopenia with a potential increased risk of bleeding; (3) anemia; (4) gastrointestinal (GI) toxicity resulting in stomatitis/mucositis, nausea, vomiting, anorexia, abdominal pain, dyspepsia, diarrhea, dehydration, and potentially mucosal/GI bleeding, and sepsis; (5) alopecia; (6) asthenia/fatigue; and (7) fever, and (8) benzodiazepine-like effects including sedation, somnolence, sleep disorders, confusion, disorientation and associated memory loss and gait disturbances (which were reversible in clinical studies with cessation of treatment or dose reduction). Skin changes including hand-foot syndrome have been reported in some patients. Clinical safety data includes experience from patients who received multiple cycles followed by treatment-free periods between each cycle, and from patients who reduced or discontinued treatment. Based on the available clinical data, drug abuse, dependency, and withdrawal were not observed.

While these toxicities are potentially associated with risk or discomfort to the patient, they are anticipated to be reversible. MLN8237 has not led to major neurotoxicities or fluid retention as a single agent. However, because there is only limited human experience with MLN8237, it is possible that MLN8237 will have other toxicities that have not been observed in or predicted from its evaluation in rats and dogs and from ongoing studies in humans. MLN8237 has a low potential to prolong the QT interval in vivo based upon its extremely weak in vitro binding to hERG (IC_{50} and K_i both $> 100 \mu M$).

To mitigate the inherent risks in clinical studies of MLN8237, patients are evaluated frequently while they are receiving treatment.

Because MLN8237 inhibits Aurora A kinase, it is possible that MLN8237 may interfere with cancer growth and cause cancer cell death through a potentially non-cross resistant pathway as compared to

other agents the patients may have received. The clinical utility of these effects will be investigated in current and future studies.

This study will be conducted in compliance with the protocol, applicable regulatory requirements, and International Conference on Harmonisation (ICH) Good Clinical Practice (GCP), guidelines.

1.4. Correlative Studies Background.

Blood: Shedding of circulating tumor cells (CTCs) into the circulation is common in advanced prostate cancer. The CellSearch (Veridex LLC, Warren, NJ) automated enrichment system capture device is an FDA-cleared technology for detecting and quantifying EpCAM expressing tumor cells in the blood and has prognostic value. A CTC count ≥ 5 per 7.5 mL of blood is considered unfavorable and <5 is favorable; furthermore, changes in CTC count on therapy is reflective of prognosis and therefore serial CTC counts are being validated prospectively as alternative biomarker of tumor response for patients with advanced prostate cancer. CTC counts by CellSearch are encouraged as part of this study, but are not mandatory. Blood will also be obtained on day 1 of each cycle and evaluated for neuroendocrine markers (serum chromogranin and NSE), lactate dehydrogenase (LDH), and prostate specific antigen (PSA).

In addition, blood for research (plasma and PBMC's) will be collected for research on C1D1, C1D8, and at progression or end of study. Plasma DNA will be evaluated for Aurora A and N-myc amplification and correlated with response to therapy and tumor tissue status. In addition, we will evaluate for concordance between plasma DNA molecular alterations and matched primary prostate cancer tissue and metastatic samples. We will correlate these results with clinical response to MLN8237.

Archival Tissue: Formalin fixed paraffin embedded (FFPE) archival prostate tumor tissue will be obtained from all patients (prostatectomy specimens or prostate biopsies) and evaluated for AR, ERG, aurora kinase A, N-myc protein expression, copy number changes, and/or translocation (in case of ERG). We hypothesize that high-risk primary prostate tumors harbor genetic alterations that predispose to clinical progression and the development of NEPC. Using the MiSeq technology (Illumina), we will perform targeted exome sequencing of matched primary tumors from 30 patients that later developed

metastatic NEPC. We will take a focused approach to examine non-synonymous recurrent mutations in FFPE tissue. Through molecular classification and correlation with clinical features and between matched primary tumors and metastases, we will gain insight into genetic alterations that arise early and predispose to the development of NEPC and will correlate with outcomes and clinical response to MLN8237.

Metastatic Tissue: A tumor biopsy of metastatic site is required for all patients and will also be evaluated for AR, ERG, aurora kinase A, N-myc protein expression, copy number changes, and/or translocation (in case of ERG). Biopsy is performed for research and must be performed prior to Cycle 1 Day 1, but results not needed before proceeding. We will perform exome and transcriptome sequencing of approximately 30 metastatic tumors from patients enrolled on study. We will determine the spectrum of mutations associated with NEPC, and compare to >150 localized prostate cancer whole exomes (n=120) and whole genomes (n=30) that we recently sequenced in collaboration with the Broad Institute. Highly ranked and potential driving mutations will be integrated with gene expression data (RNA-Seq) and protein expression (IHC) and correlated with clinical features, treatment response to MLN8237, and outcomes. We will generate a comprehensive genetic profile and characterize the spectrum of actionable and informative mutations in NEPC. An optional metastatic biopsy at time of progression will be obtained in consenting patients; these tumors will be evaluated for molecular changes associated with progression on MLN8237.

Extensive genomic profiling of metastatic and primary tumor specimens will help establish novel prognostic biomarkers and those that may predict response to MLN8237. This study will also identify molecular alterations associated with disease progression and treatment resistance, bring new insight into the mutational spectrum of advanced disease, and identify additional therapeutic targets. We hypothesize that advanced prostate tumors acquire driving mutations in response to therapy that allows them to evade therapy and transform to a NEPC phenotype.

2.0 Study objectives

2.1 Primary objectives

- The primary endpoint is the proportion of patients who are free from radiographic progression at 6 months following treatment with MLN8237.

2.2 Secondary objectives

- To determine the overall survival with MLN8237
- To evaluate the objective response rate
- To determine the progression free survival with MLN8237
- To determine the PSA response rate with MLN8237
- To determine baseline and changes in circulating tumor cell count in response to therapy and at disease progression
- To determine serum neuroendocrine marker response with MLN8237

2.3 Exploratory Objectives

- To determine Aurora kinase A and N-myc gene amplification status plasma DNA at baseline and correlate with archival and metastatic tumor Aurora kinase A and N-myc status, other pathologic findings (neuroendocrine markers, AR status), and correlate with response to therapy with MLN8237
- To evaluate for Aurora kinase A and N-myc overexpression and amplification in archival and metastatic tumor tissue and correlate with other pathologic findings (including neuroendocrine markers, AR status, ERG status), and correlate with response to therapy with MLN8237

3.0 Study design. This is a multi-institutional single-arm, open-label Phase 2 trial evaluating MLN8237 in patients with histologically confirmed or clinically suspected neuroendocrine prostate cancer (see inclusion criteria for full list of eligibility). Subjects will be treated with MLN8237 at 50 mg twice daily for 7 days repeated every 21 days. Individual dose reductions will be made on the basis of the AEs observed. Therapy will continue until disease progression, unacceptable toxicity as a result of MLN8237, or withdrawal of patient consent. Patients will be followed with history, physical, and blood tests at each visit to monitor for toxicity. Response and progression will be evaluated by CT/MRI scan and bone scan every 3 cycles and determined using RECIST v1.1 with PCWG2 modifications. PSA and serum chromogranin A and NSE will be followed every cycle. CTC counts will be performed at baseline, at 4-6 weeks, and upon progression. Patients will be followed for survival endpoints following completion of this study until death.

4.0 Subjects

4.1 Recruitment. These patients will be recruited from the existing and referred patient population at Weill Cornell Medical College (WCMC)-New York Presbyterian Hospital (NYPH) and additional institutions.

Patients are initially chosen based on a) MD evaluation; b) outpatient interview; c) criteria for inclusion and exclusion (as described below). This study will be explained to the patient in the physician's office or other appropriate professional setting. The patient will be given a copy of IRB approved written consent form to take home for a thorough reading and consideration. Should the patient wish to enter the study, he will return to physician's office for further discussion and to complete the informed consent process. Only the investigators will obtain a subject's informed consent.

4.2 Number of patients. Up to 60 patients will be treated, with at least 30 patients requiring histologically proven NEPC (Inclusion criteria 4.3.1.1 or 4.3.1.2). While all registered subjects will be included in the final intent to treat analysis, only subjects who receive at least one dose of study drug will be considered eligible to toxicity analysis. Subjects who are enrolled, but do not complete at least one planned cycle with MLN8237 may be replaced.

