8.10 Termination of Treatment and/or Study Participation

Patients will be informed that they have the right to withdraw from the study at any time for any reason, without prejudice to their medical care. The investigator will withdraw patients from the study for any of the following reasons:

- Occurrence of an unacceptable adverse event
- A treatment cycle delay of >3 weeks because of toxicity
- Patient request
- General or specific changes in the patient's condition unacceptable for further treatment in the judgment of the investigator
- Progressive disease at any time

At the time of withdrawal, all study procedures outlined for the End of Study visit should be completed. The primary reason for a patient's withdrawal from the study is to be recorded in the source documents.

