- Withdrawal of patient consent
- Noncompliance with protocol-specified procedures which in the opinion of the investigator will expose subjects to undue risk or will significantly effect interpretation of study results

12. Statistical Considerations.

12.1. Sample Size Justification:

The primary endpoint is the proportion of patients who are free from radiographic progression at 6 months following treatment with MLN8237. Based on the phase II trial by Meulenbeld et al (BJUI 2012), the proposed null hypothesis (H_0) is that $\leq 15\%$ of patients will be radiographic progression-free at 6 months and the alternative hypothesis (H_a) is that $\geq 30\%$ of patients will be radiographic progression-free at 6 months.

Sample size recommendations for the phase II design are determined according to Ahern's exact single-stage phase II design (A'Hern RP, 2001). We project a 6-month radiographic progression-free proportion of 15%, below which the response will be unacceptable, and a 6-month radiographic progression-free proportion of 30%, above which the regimen will be considered worthy of further exploration. The null hypothesis that the 6-month radiographic progression-free proportion is less than or equal to 15% will be tested against the alternative hypothesis that the 6-month radiographic progression-free proportion is greater than or equal to 30%.

The sample size computations were performed assuming a 5% level of significance and 80% power. A total of 48 patients will be required to enroll in the study. The treatment will be declared effective and worthy of further testing if 12 or more patients are free from radiographic progression at 6 months among the 48 patients entered into the study. This exact single-stage design yields a ≥ 0.80 probability of a positive result if the true percentage of patients who are free from radiographic progression at 6 months is $\geq 30\%$. It yields a ≥ 0.95 probability of a negative result if the true percentage of patients who are free from radiographic progression at 6 months is $\leq 15\%$. Assuming 10-20% of patients will be unevaluable/ineligible, we anticipate that a total 60 patients will be enrolled in the study.

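### Section 4.2 allows replacement of any subject who does not complete cycle 1, whatever the cause or dosing, and this is not reconciled with its intent-to-treat sentence or with the 12-of-48 success rule

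*Protocol*

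**What the plan says.** Section 4.2 of the protocol sets the replacement rule: "Subjects who are enrolled, but do not complete at least one planned cycle with MLN8237 may be replaced". It names no cause and draws no line between subjects who took drug and subjects who did not. The sentence before it begins "While all registered subjects will be included in the final intent to treat analysis" and goes on to restrict the toxicity analysis to subjects with at least one dose. That dosed/undosed distinction is not carried into the replacement rule.

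Section 12.1 (repeated in the protocol summary) gives the decision rule. The design is "determined according to Ahern's exact single-stage phase II design", with a null proportion of 15% and an alternative of 30% free from radiographic progression at 6 months. Success is 12 or more among 48 patients entered. It continues: "Assuming 10-20% of patients will be unevaluable/ineligible, we anticipate that a total 60 patients will be enrolled in the study". The protocol does not say what makes a patient unevaluable, whether a replaced patient counts among the 48, or what cutoff applies if more than 48 are analysed. The primary-endpoint paragraph that follows names no analysis set.

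Section 8.10 lists reasons for withdrawal, among them "Occurrence of an unacceptable adverse event" and progressive disease at any time. Either can occur in cycle 1.

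**The concern.** Not completing one 21-day cycle can be a result of the treatment or of the disease. A treated patient who progresses or dies in that window cannot be progression-free and alive at 6 months, yet the rule allows him to be replaced. The trial is open-label and replacement is optional, so whoever decides knows why the patient stopped.

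At stake is the only go/no-go decision in an uncontrolled trial. Depending on how replaced patients are counted, either the 6-month proportion describes only patients who got through cycle 1, or the denominator grows while the required number of successes stays fixed. The claimed 95% probability of a negative result at a true 15% fails either way. Who may be replaced is an enrolment rule that sites apply during accrual. The protocol itself fixes it, so it cannot simply be left to a later analysis plan.

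**Working it through.** **Inputs.** From section 12.1: p0 = 0.15, p1 = 0.30, 5% significance, 80% power, n = 48, cutoff r = 12, and an allowance of 10-20% leading to 60 enrolled. The hypotheses are one-sided in form. Not in the protocol: f, the share of dosed patients who fail in cycle 1 and are replaced. It is assumed here to lie between 2% and 20%; the upper end borrows the top of the protocol's allowance, which covers a wider group.

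**Step 1: the plan's own figures.** With X ~ Binomial(n, p), the exact tail P(X ≥ 12 | n = 48) is 0.0478 at p = 0.15 and 0.819 at p = 0.30. A search over n shows 48 is the smallest size meeting both limits. The allowance also reproduces: 48/(1 − 0.20) = 60 and 48/(1 − 0.10) = 53.3, rounded up to 54. The design is correct as stated, but its margin is small: 4.78% against 5%.

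**Step 2: replaced failures leave the 48.** Of N dosed patients, pN are progression-free at 6 months. If a fraction f all fail in cycle 1 and are all replaced and dropped, every success lies among the remaining (1 − f)N. The proportion in the retained set is therefore p/(1 − f). With p = 0.15:

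| f (assumed) | 0.15/(1 − f) | P(X ≥ 12 of 48) |
|---|---|---|
| 0 | 15.0% | 4.8% |
| 2% | 15.3% | 5.4% |
| 5% | 15.8% | 6.6% |
| 10% | 16.7% | 9.2% |
| 20% | 18.75% | 17.6% |

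**Step 3: replaced patients stay in and the cutoff stays at 12.** The proportion among all registered patients is not biased by replacement, but the number of chances to reach 12 grows. At p = 0.15:

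| Rule | Type I error |
|---|---|
| 12 of 48 | 4.8% |
| 12 of 49 | 5.5% |
| 12 of 54 | 10.1% |
| 12 of 60 | 18.1% |

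One added patient is enough to pass 5%.

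**Step 4: cutoffs matched to the denominator.** For 60 analysed, 14 gives a type I error of 5.8%, which is too high; 15 gives 2.9% with power 83.8%. Not every n has a cutoff that meets both limits: at 54, a cutoff of 13 gives 5.3%, and 14 gives 2.6% with power 78.6%.

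**The case against.** The strongest reply is the intent-to-treat sentence in section 4.2. Read literally, a replaced subject stays in the final analysis, replacement only adds patients, and the proportion has no upward bias. Nowhere does the protocol say that replaced subjects leave the primary analysis. This stands. A reader might infer that the primary estimate is biased upward by design; the documents do not support that, because the bias depends on an analysis set that the primary-endpoint paragraph does not name. The reply does not rescue the decision rule, however, since no cutoff is given for more than 48 patients (step 3).

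A reader might also infer that every cycle-1 stop is a certain failure. That is not supported for toxicity. The endpoint is radiographic, and a patient who stops for toxicity has not necessarily progressed. The first scheduled scan is after cycle 3, so radiographic progression documented in cycle 1 would need an unscheduled scan.

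The sizes in step 2 are an upper bound for each f: every such patient is taken to fail, to be replaced although replacement is optional, and to be dropped. The 10-20% allowance covers all unevaluable or ineligible patients, not only cycle-1 failures. Entry also requires an estimated life expectancy above 3 months and ECOG 0-2, which should keep very early deaths down.

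Finally, early toxicity would not be hidden from the safety results, because section 4.2 keeps every subject with at least one dose in the toxicity analysis.

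**Conclusion.** The point holds as a conditional defect and should be fixed. The replacement rule, the intent-to-treat sentence and the 12-of-48 rule cannot all be applied together as written, and both ways of resolving them break the stated 5%.

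If replaced cycle-1 failures are dropped, the proportion can be inflated by 1/(1 − f), and the type I error is 5.4% to 17.6% for f of 2% to 20%. This rests on the assumed f and on the worst-case handling described above. If replaced patients are kept with a cutoff of 12, the proportion is not biased by replacement and the type I error runs from 5.5% (49 analysed) to 18.1% (60 analysed). That second result needs no assumption about f, only about how many patients are analysed.

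The documents do not show which reading was intended, so neither an actual bias nor its actual size can be claimed.

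**What to change.** In section 4.2, replace the last sentence with wording to this effect: only subjects who receive no dose of MLN8237 may be replaced; every subject who receives at least one dose stays in the denominator of the primary endpoint and is not replaced. Add the counting rule: early progression, death, or no evidence of being progression-free at 6 months counts as not progression-free, while a toxicity stop alone is not a failure if later imaging shows no progression at 6 months.

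Align the intent-to-treat sentence with this by saying whether registered but never-dosed subjects enter the primary analysis. In section 12.1, state a cutoff that matches the number actually analysed: 12 of 48 (type I error 0.048, power 0.819) or, for example, 15 of 60 (0.029 and 0.838). Because some sizes between these, such as 54, have no cutoff meeting both limits, the rule should be set out in advance for each possible denominator.

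The cost is a few sentences in an amendment and no extra patients. The reported proportion may be slightly lower than under replacement.
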